9.1.5 Definition of Unacceptable Toxicity

Toxicities will be graded according to the NCI CTCAE version 4 criteria. Any Grade 3 or any Grade 4 toxicity that is not reversible within 2 weeks, any life-threatening event deemed related to the study drug, or any treatment-related death will be considered unacceptable.

Any Grade 2 or higher autoimmune toxicities, particularly those affecting vital organs (e.g. cardiac, renal, CNS), will be considered an unacceptable toxicity, if it occurs within 2 weeks post-infusion. Grade 3 or higher surgical complications from insertion of the catheter are considered an unacceptable toxicity.

Exceptions to these unacceptable toxicities are as follows:

- Events associated with the biopsy procedure/catheter placement: Seizures or hemorrhages occurring during anesthesia or the biopsy/catheter insertion proper prior to administration of the agent if Grade 2 or lower.
- Seizures: Due to the nature of the disease under investigation in this protocol, patients may have pre-existing seizures or be susceptible to new seizures as a result of the underlying disease process. Although seizures may be defined as Grade 3 or 4 toxicities under NCI CTC, and will be reported as such in this protocol, seizures will not be considered an unacceptable toxicity if, in the opinion of the site Principal Investigator they have not increased in frequency or can be attributed to another recognized cause of increasing seizure frequency such as sub-therapeutic anti-convulsant levels or biopsy proven tumor progression.
- New or worsening neurologic deficits: Due to the nature of the disease under investigation in this protocol, patients may have an increase in pre-existing neurologic deficits or may develop new neurologic deficits as a result of tumor invasion. A new neurologic deficit, which resolves within 2 weeks after initiation of medical therapy, will not be considered an unacceptable toxicity. New neurological symptoms will not be an unacceptable toxicity if they can be ascribed to tumor progression (e.g. documented with histopathologic analyses of biopsy tissue), or they respond to treatment (e.g. oral steroids) within 2 weeks.

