- Thromboembolism: While deep vein thrombosis (DVT) is not as common in children as in adults with malignant glioma, patients may have undiagnosed pre-existing DVTs or be susceptible to the development of DVTs due to the underlying disease process. Although DVT may be defined as Grade 3 or 4 toxicities under NCI CTC, and will be reported as such in this protocol, DVT will not be considered an unacceptable toxicity in this protocol.
- Syndrome of Inappropriate Antidiuretic Hormone (SIADH): Due to the high incidence of SIADH in this patient population, patients may be susceptible to the development of SIADH due to the underlying disease process. Although SIADH may be defined as Grade 3 toxicity under NCI CTC, and will be reported as such in this protocol, SIADH will not be considered an unacceptable toxicity in this protocol unless it is refractory to medical management.
- Muscle Weakness and Weight Gain: Due to the high incidence of muscle weakness and weight gain in patients taking steroids in this patient population, patients may be susceptible to the development of muscle weakness or weight gain which is due to steroids alone. Although muscle weakness may be defined as Grade 3 or 4 toxicity and weight gain $\geq 20\%$ may be defined as Grade 3 toxicity under NCI CTC, and will be reported as such in this protocol, muscle weakness or weight gain will not be considered an unacceptable toxicity in this protocol if the patient has required steroids greater than physiologic doses in the interval between the immunization and the development of the toxicity.

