9.1.6 Safety Considerations

- Surgical Complications: The stereotactic tumor biopsy and catheter implantation procedure carries a risk for cerebrospinal fluid leak, infection, hemorrhage, loss of neurologic function, non-neurologic complications and death. These risks depend primarily on the preoperative condition of the patient, the size and location of the tumor and associated diseases. The potential risk for the patient will be discussed in detail with the patient and family.
- Anesthesia: Patients undergoing general anesthesia may be subjected to associated risks including pneumothorax, pneumonia, airway injury, hypotension, myocardial infarction, stroke, hepatic and renal injury and death.

- **Poliomyelitis:** PVSRIPO has been tested in non-human primates according to the WHO standardized monkey neurovirulence tests. These tests revealed the absence of neuropathogenic properties, evident as failure to induce symptoms of poliomyelitis in non-human primates after intracerebral inoculation of virus. However, PVSRIPO is a replication-competent viral agent that, in principle, retains the potential to cause motor neuron damage. Possible complications include transient or permanent mono- or paraparesis, paralysis, and life-threatening respiratory insufficiency.
- **Virus Recombination and Mutation:** PVSRIPO retains the ability to alter its genome during replication upon administration to patients. Various mechanisms are known to lead to genetic adaptation, including spontaneous mutagenesis and recombination that may give rise to viral progeny with changed properties. Empirical studies in tissue culture and laboratory animals demonstrated that prolonged passaging in GBM cells does not select for genetic changes in viral progeny. However, the occurrence of such events cannot be categorically excluded in patients receiving intracerebral PVSRIPO. Genetic changes may cause an altered phenotype of PVSRIPO, including adaptation to improved virus replication in the normal CNS.

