11 SUBJECT ELIGIBILITY

11.1 Inclusion Criteria

1. Patients must have a recurrent supratentorial WHO Grade III malignant glioma (anaplastic astrocytoma, anaplastic oligoastrocytoma, anaplastic oligodendrogloma, anaplastic pleomorphic xanthoastrocytoma, ependymoma) or WHO Grade IV malignant glioma, medulloblastoma, or atypical teratoid/rhabdoid tumor (ATRT) based on imaging studies with measurable disease (≥ 1 cm and ≤ 5.5 cm).

- a. The prior histopathology must be consistent with a World Health Organization (WHO) Grade III or IV malignant tumor confirmed by the study pathologist, [name], or his designee.
- b. The tip of the infusion catheter can be placed \geq 1cm from any ventricle.
- 2. There is no standard of care treatment for children with Grade III/IV gliomas; however, patients must have received some form of definitive treatment, i.e., standard therapy with known clinical benefit, for their initial diagnosis prior to their recurrence/progression. Definitive treatment includes maximal safe resection (if possible) and radiation therapy with or without chemotherapy. (*Please note that patients who are unable to receive radiation therapy due to genetic disorders that put them at significant risk for radiation-induced secondary malignancies (i.e., Gorlin's syndrome or NF1 mutation) are still eligible to participate.*)
- 3. All patients must be \geq 4 years of age and \leq 21 years of age at the time of entry into the study.
- 4. The patient must have a Lansky or Karnofsky Performance Score (KPS) of \geq 70% at the time of entry.
- 5. Laboratory Studies:
 - a. Platelet count \geq 125,000/ μ l prior to biopsy. Platelets \geq 100,000/ μ l prior to infusion;
 - b. Prothrombin and Activated Partial Thromboplastin Times \leq 1.2 x upper limit of normal (ULN) prior to biopsy;
 - c. Positive serum anti-poliovirus titer \geq 1:8 prior to biopsy;
 - d. Creatinine \leq 1.2 x ULN prior to biopsy;
 - e. Total bilirubin, AST, ALT, alkaline phosphatase \leq 2.5 x ULN prior to biopsy;
 - f. Neutrophil count \geq 1000 / μ l prior to biopsy;
 - g. Hemoglobin \geq 9 gm/dl prior to biopsy (can be transfused).
- 6. The patient must have received a boost immunization with trivalent inactivated IPOL™ (Sanofi-Pasteur) \geq 1 week prior to administration of the study agent.
- 7. At the time of biopsy, prior to administration of virus, the presence of recurrent tumor must be confirmed by histopathological analysis.

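### The muscle-weakness exception in Section 9.1.5 turns on steroid exposure, not cause, so virus-related Grade 3-4 weakness can drop out of the primary endpoint and the Table 4 suspension count

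*Combined protocol and SAP*

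**What the plan says.** Section 9.1.5 defines unacceptable toxicity. Its general rule includes "Any Grade 3 or any Grade 4 toxicity that is not reversible within 2 weeks", with further limbs for related life-threatening events, treatment-related death, autoimmune toxicity and surgical complications. A list of exceptions follows.

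The last exception covers muscle weakness and weight gain. Its rationale is "muscle weakness or weight gain which is due to steroids alone". It concedes the severity ("Although muscle weakness may be defined as Grade 3 or 4 toxicity") and says that such events "will be reported as such in this protocol". The operative clause then reads "muscle weakness or weight gain will not be considered an unacceptable toxicity in this protocol if the patient has required steroids greater than physiologic doses". The period over which that steroid exposure is looked for is given as "in the interval between the immunization and the development of the toxicity".

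A separate exception covers new or worsening neurologic deficits. It exempts a deficit that resolves or responds to treatment within 2 weeks, or that is ascribed to tumour progression. Steroid use alone does not exempt it.

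Section 9.1.6, under poliomyelitis, says that "PVSRIPO is a replication-competent viral agent that, in principle, retains the potential to cause motor neuron damage". It lists paresis, paralysis and respiratory insufficiency as possible complications.

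The Section 9.1.5 definition feeds the primary endpoint (Table 1 and Section 15.4.2) and the acute suspension rule (Section 15.4.1, Table 4).

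**The concern.** The rationale is about cause; the test is about exposure. Under the operative clause nobody has to judge that steroids caused the weakness. There is no carve-out for weakness suspected to come from the virus, although that is a motor risk the protocol names itself.

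The exposure interval is also undefined at its start. The word immunization is used elsewhere for the polio booster: Section 11.1, criterion 6 says "The patient must have received a boost immunization with trivalent inactivated" vaccine at least 1 week before the study agent, and Section 12.1 allows it within 6 months before infusion. If the booster is meant, steroids needed and stopped before any virus exposure would satisfy the condition. If the PVSRIPO infusion is meant, the text does not say so.

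The primary objective of this trial, with at most 12 patients, is safety. One or two misclassified events change both the reported percentage and whether accrual is suspended.

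**Working it through.** **1. The passages side by side.** Take a patient with Grade 3-4 limb weakness within 14 days that does not reverse within 2 weeks, is not ascribed to progression, and follows supraphysiologic steroid use in the stated interval.

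- General rule: counts.
- Classed as a neurologic deficit: counts, because it neither resolved nor responded within 2 weeks.
- Classed as muscle weakness: does not count, whatever its cause.

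The exceptions are parallel bullets with no order of precedence, so the chosen term decides.

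**2. Effect on Table 4, with no assumed rate.** For up to 6 patients accrued, the threshold is 2 or more. Two such events give a count of 2 (suspend) if classed as neurologic deficits, and 0 (continue) if both are classed as exempt muscle weakness.

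**3. Reproducing Table 5.** Suspend at 2 or more events for n up to 6, 3 or more for n = 7-9, and 4 or more for n = 10-12, with a maximum of 12 patients. The count never falls and the threshold is constant within each band, so

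P(suspend) = 1 − P(X6 ≤ 1, X9 ≤ 2, X12 ≤ 3).

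At p = 0.20:
- P(X6=0) = 0.8^6 = 0.2621; P(X6=1) = 6 × 0.2 × 0.8^5 = 0.3932.
- Three further patients give 0, 1, 2 or 3 events with probability 0.512, 0.384, 0.096, 0.008.
- Not suspended by n = 9: X9=0: 0.1342; X9=1: 0.3020; X9=2: 0.1762.
- Not suspended by n = 12: 0.1342 + 0.3020 × 0.992 + 0.1762 × 0.896 = 0.592.
- P(suspend) = 0.408. Table 5 gives 0.411.

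| True rate | Table 5 | Recomputed |
|---|---|---|
| 0.05 | 0.030 | 0.035 |
| 0.10 | 0.124 | 0.128 |
| 0.15 | 0.262 | 0.259 |
| 0.20 | 0.411 | 0.408 |
| 0.25 | 0.560 | 0.555 |
| 0.30 | 0.681 | 0.686 |
| 0.35 | 0.792 | 0.793 |
| 0.40 | 0.873 | 0.872 |

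The largest gap is 0.005. Expected accrual, checked after every patient, agrees within 0.1. Table 5 is therefore sound for events that are counted; exempted events lie outside it.

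**4. Illustration under assumed rates.** With a total rate of 20% and half the events exempt, the counted rate is 0.20 × (1 − 0.5) = 0.10. The suspension probability falls from 0.408 to 0.128, and expected accrual rises from 9.2 to 11.1. The same drop can be read directly from Table 5 (0.411 to 0.124).

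To separate the sources, let o be the rate of other unacceptable toxicity, m the rate of persistent Grade 3-4 weakness (taken as occurring in different patients), and s the exempt share of weakness events. The counted rate is o + m(1 − s). Suspension probability, with expected accrual in brackets:

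| o | m | s = 0 | s = 0.5 | s = 1 |
|---|---|---|---|---|
| 5% | 5% | 0.128 (11.1) | 0.075 (11.5) | 0.035 (11.8) |
| 5% | 10% | 0.259 (10.2) | 0.128 (11.1) | 0.035 (11.8) |
| 5% | 20% | 0.555 (8.1) | 0.259 (10.2) | 0.035 (11.8) |
| 10% | 10% | 0.408 (9.2) | 0.259 (10.2) | 0.128 (11.1) |

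The documents give no value for o, m or s.

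**The case against.** The strongest reply is that the neurologic-deficit exception already handles paresis. Mono- or paraparesis and paralysis are ordinarily neurologic deficits. Pairing muscle weakness with weight gain suggests that the last exception is meant for steroid myopathy. Respiratory insufficiency is not named in that exception, and the general rule separately counts related life-threatening events and treatment-related deaths. This stands as a likely reading of intent, but the text does not secure it: no precedence is stated, and the operative clause covers Grade 3-4 weakness of any origin.

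A second reply is that nothing is concealed. Exempted weakness is still reported at its grade, Section 15.4.2 tabulates all adverse events by maximum grade, Section 13.1.2 provides for trend review, SAEs reach the sponsor within 24 hours (Section 13.2.1), and the DSMB-Plus can recommend stopping (Section 13.7). This also stands. It does not put the event back into the primary percentage or the Table 4 count. The long-term rule covers only inflammatory reactions, and Section 13.1.1 lists no events of special interest.

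A third reply concerns size. Section 7.2.6 reports 61 adults treated in Phase I, and Section 7.3 reports no evidence of poliomyelitis in that trial. If that statement covers all 61 (an assumption), the one-sided 95% upper bound is 1 − 0.05^(1/61) = 4.8%, near the lowest weakness rate in the table above. Section 7.2.6 also says that adults at the dose used here could stay off significant steroid doses, so the exposed share may be small. On the other side, adult data may not carry over to children. Section 11.2 does not exclude dexamethasone up to 4 mg/day at entry, and the limit on raising it in Section 9.1.6 applies only after the first 2 weeks. The size is therefore open.

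**Conclusion.** The exception is wider than its own rationale. It can remove persistent Grade 3-4 weakness caused by the virus from the 14-day primary endpoint and from the acute suspension count. That conclusion, and the 2-versus-0 example, rest on the text alone. The fall from about 0.41 to 0.13 is only an illustration. It assumes independent patients, a 20% total rate and half of the events exempt; the size in this trial cannot be known from the documents.

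A reader might go further and infer that the exception hides the agent's motor risk, so that several cases of limb paralysis could pass with no action. The documents do not support that: such events stay in adverse event tables, SAE reports and DSMB-Plus review, and those classed as neurologic deficits can still count. Nor do the documents establish that steroids taken before infusion trigger the exemption; that holds only if immunization means the booster, and the word is undefined.

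**What to change.** Amend the muscle-weakness paragraph of Section 9.1.5 in three respects:

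- Exempt Grade 3-4 weakness only when the investigator assesses and documents it as due to steroids alone. Judge any other weakness under the general rule and the neurologic-deficit exception.
- State that the neurologic-deficit exception governs paresis and paralysis, and reconcile both exceptions with the poliomyelitis risk in Section 9.1.6.
- Replace immunization with a defined start point: the PVSRIPO infusion, if that is what was meant. Weight gain shares this clause, so the change applies to it too.

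The cost is a one-paragraph change to an endpoint definition, with no change to patient care and no new assessments. Neurologic exams are already scheduled daily until discharge and at weeks 1 and 2 (Section 12.4). Exclusion 12 already asks investigators to recognise worsening steroid myopathy, so attribution is a judgement the protocol relies on. The downside is that the reported unacceptable-toxicity rate may be slightly less favourable.

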 - b. Patients who have received chemotherapy or bevacizumab ≤ 4 weeks [except for nitrosourea (6 weeks) or metronomic dosed chemotherapy such as daily etoposide or cyclophosphamide (1 week)] prior to starting the study drug unless patients have recovered from side effects of such therapy.
 - c. Patients who have received immunotherapy ≤ 4 weeks prior to starting the study drug unless patients have recovered from side effects of such therapy.
10. Patients with neoplastic lesions in the brainstem, cerebellum, spinal cord, intraventricular tumors, pituitary tumors, leptomeningeal disease, or other locations at the discretion of the treating neurosurgeon.
11. Patients with a diagnosis of agammaglobulinemia, that is:
 - a. Undetectable anti-tetanus toxoid IgG
 - b. Known history of agammaglobulinemia
12. Patients who are on dexamethasone receiving > 4 mg/day in the two weeks prior to admission for intra-cerebral delivery of PVSRIPO or who demonstrate worsening steroid myopathy.
13. Patients with prior, unrelated malignancy requiring current active treatment with the exception of cervical carcinoma *in situ* and adequately treated basal cell or squamous cell carcinoma of the skin.

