12 SCREENING AND ON-STUDY TESTS AND PROCEDURES

Table 2. Schedule of Study Tests and Procedures

Description	Within 6 months	Screening: Within 14 days prior to catheter placement	Screening: Within 5 days prior to PVSRIPO	Catheter Placement biopsy, PVSRIPO infusion	After Completion of Infusion	Post infusion (follow-up period) ^a						
Week						0	1	2	4	8	16, 24, 32, 40, 48	
Day		Within 14 days prior to catheter placement	Within 5 days prior to PVSRIPO	0	0	1	7	14	28	56	112, 168, 224, 280, 336	
General Evaluations												
Physical Exam		X	X			X ^b	X	X	X	X		X
Neurologic Exam		X	X			X ^b	X	X	X	X		X
Performance Status		X	X				X	X	X	X		X
Adverse Events ^h	X	X	X			Continuous						
Laboratory Evaluations												
Poliovirus Immunization Booster	X											
CBC w/diff		X				X		X	X	X		X
CMP		X				X		X	X	X		X
PT, aPTT		X										
Serum Pregnancy Test		X	X ^c									
Serum for LSQ and anti-tetanus toxoid IgG	X											
Whole blood for immunologic analysis and/or poliovirus titer (up to 10 mL, except for 4 mL on Day 1 and 6 mL on Day 14)	X	X				X	X	X	X	X	X (at 16 and 24 wks) ^d	
Whole blood for immunologic analysis (not to exceed 3 mL/kg in a 24 hr period or 7 mL/kg in a 8 week period)	X ^e	X ^e					X ^e	X ^e	X ^e	X ^f	X (at 16 and 24 wks) ^{d, f}	
Disease Evaluations												
MRI			X		X ^g (based upon date of enrollment)				X	X		X
CT Scan				X								
Biopsy				X								
Treatment												
PVSRIPO				X								

^a Starting with Day 7 (Week 1), all tests and procedures have a 7-day plus or minus window.

^b Daily after infusion until discharged from hospital

^c Serum pregnancy test, if appropriate, within 48 hours of catheter placement and PVSRIPO

^d At the discretion of the Principal Investigator, an additional blood sample at least 2 years post study drug infusion may be obtained.

^e Whole blood draws for immunologic analysis may be taken (up to 36 mL) at the discretion of the Investigator, but should remain consistent with allowable volumes for pediatric patients depending upon the weight of the child (per Duke policy, the maximum blood volume drawn for research should not exceed 3 mL/kg in a 24 hr period or 7 mL/kg in an 8 week period).

^f At 8, 16, and 24 weeks, up to 76.5 mL of whole blood may be drawn for immunologic analysis (please refer to Duke blood volume policy mentioned above).

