12.1 Screening Examination

The screening examination will take place within 2 weeks before catheter placement. An informed consent must be signed by the patient and their legal guardian(s) before any study-specific screening procedure takes place. Within 6 months before receiving the PVSRIPO infusion, the patient should have received a PV booster, a serum test for LSQ and anti-tetanus toxoid IgG. The patient should also have whole blood drawn (up to 10 mL; red top tube(s)) for immunologic analysis and PV titer and an additional amount (up to 36 mL; yellow top ACD tube(s)) for other immunologic analysis during this time. Blood volumes drawn for immunologic analyses should not exceed 3 mL/kg in a 24 hour period or 7 mL/kg in an 8 week period, allowable per Duke policy. At the discretion of the investigator, blood volumes for immunologic analysis should be adjusted depending upon the weight of the child, in order to be consistent with Duke policy.

Pre-treatment evaluations within 2 weeks before catheter placement to determine eligibility and as a baseline will include the following, unless otherwise indicated:

- History and physical exam, including a full neurologic assessment and KPS or Lansky, within 2 weeks of catheter placement and within 5 days of PVSRIPO infusion
- Laboratory Evaluations:
 - CBC with differential
 - CMP
 - PT, aPTT
 - Beta-HCG, if appropriate (within 48 hours of catheter placement and PVSRIPO)
 - Anti-tetanus toxoid IgG (within 6 months of catheter placement and PVSRIPO)
 - LSQ (within 6 months of catheter placement and PVSRIPO)
 - Whole blood (up to 10 mL) for immunologic analysis and poliovirus titer
 - Whole blood (up to 36 mL, but not to exceed 3 mL/kg in a 24 hour period or 7 mL/kg in an 8-week period) for immunologic analysis (volumes drawn will be adjusted at the discretion of the Investigator, but will be based on the weight of the child to be consistent with Duke policy)
- Baseline MRI of the brain within 5 days of starting treatment

If a subject does not receive PVSRIPO, minimal records regarding the subject and the reason for screen failure will be retained in the study database.

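### The muscle-weakness and weight-gain exception in Section 9.1.5 counts steroid use from an undefined 'immunization'; read literally this is the polio booster, so steroids stopped before infusion could exempt a later toxicity

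*Combined protocol and SAP*

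**What the plan says.** Section 9.1.5 defines unacceptable toxicity and then lists exceptions. The last exception states that "muscle weakness or weight gain will not be considered an unacceptable toxicity in this protocol if the patient has required steroids", and it specifies the exposure as "steroids greater than physiologic doses in the interval between the immunization and the development of the toxicity". The rationale given just before is that patients in this population may develop "muscle weakness or weight gain which is due to steroids alone". Exempted events are still reported at their CTCAE grade.

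Section 9.1.5 does not define the immunization. Elsewhere the word names the polio booster:

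- Section 11.1, criterion 6: "The patient must have received a boost immunization with trivalent inactivated IPOL™", at least 1 week before the study agent. Exclusion 1 in Section 11.2 refers to the same booster.
- Section 12, Table 2: the row "Poliovirus Immunization Booster", marked in the column for the 6 months before treatment.
- Section 12.1: "Within 6 months before receiving the PVSRIPO infusion, the patient should have received a PV booster".

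Exclusion 12 in Section 11.2 bars patients on dexamethasone above 4 "mg/day in the two weeks prior to admission for intra-cerebral delivery of PVSRIPO", and also patients with worsening steroid myopathy.

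The Section 9.1.5 definition is used twice. It supplies the primary endpoint (Table 1 and Section 15.4.2: the percentage with unacceptable toxicity in the 14 days after PVSRIPO) and the accrual-suspension count in Table 4 (Section 15.4.1).

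**The concern.** The endpoint window opens at infusion, but the steroid window that can cancel an endpoint event appears to open earlier, at the booster. A patient whose only supraphysiologic steroid course fell between booster and infusion would then meet the exception, and severe weakness arising after the study drug would not count.

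Weakness matters for this agent because Section 9.1.6 names motor neuron damage, with paresis and paralysis, as a possible complication of a replication-competent virus. An exemption triggered by exposure that ended before dosing would bias the primary percentage downward and could delay a suspension.

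The start of the interval is a separate question from whether steroids must be judged the cause. Adding a causation test would still leave the interval starting at an undefined event.

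**Working it through.** **1. What the term can mean.** The only immunization the protocol requires of patients is the IPOL booster. For PVSRIPO given to patients, the protocol uses infusion, administration, inoculation, injection or instillation. Section 9.1.5 itself uses infusion and administration for its other timed criteria. The one phrase likening PVSRIPO to immunization (Section 9.1.6, household contacts) concerns accidental exposure of others. The literal reading is therefore the booster, but no sentence says so for this exception.

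**2. Length of the interval on the literal reading.** Take an event on day 14, the end of the endpoint window. Share of calendar time before infusion = booster lead time / (lead time + 2 weeks).

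| Booster given | Calculation | Share before infusion |
|---|---|---|
| 1 week before (Section 11.1 minimum) | 1/3 | 33% |
| About 4 weeks before (Table 3 sets its 6-month column at about day -28) | 4/6 | 67% |
| 26 weeks before (Section 12.1 maximum) | 26/28 | 93% |

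Table 3 schedules blood draws, so using its day -28 for the booster is an inference. These are shares of calendar time, not of steroid exposure or of events.

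**3. Do other provisions close the gap?**

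- Exclusion 12 leaves earlier courses at any dose, and dexamethasone at or below 4 mg/day in the last two weeks. Whether the latter exceeds physiologic doses is unknown, because no threshold is given.
- The steroids-alone rationale is not repeated in the operative condition, which asks only whether steroids were required in the interval.
- New or worsening neurologic deficits have their own exception, which excuses them if they resolve or respond within 2 weeks or are ascribed to tumor progression. Virus-type paresis fits there naturally. No text says which exception governs an event recorded as muscle weakness.

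**4. Effect of one misclassified event.** Maximum N is 12 (Section 15.9), so 1/12 = 8.3 percentage points at full accrual. The Table 4 thresholds are 2 events (up to 6 patients), 3 (7 to 9) and 4 (10 to 12). One exempted event turns 2 into 1, 3 into 2, or 4 into 3, and the threshold is missed.

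**5. The plan's own figure.** An exact binomial recursion over patients 1 to 12, applying Table 4 after each, reproduces Table 5.

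| True rate | Table 5 | Recomputed |
|---|---|---|
| 0.05 | 0.030 | 0.035 |
| 0.10 | 0.124 | 0.128 |
| 0.15 | 0.262 | 0.260 |
| 0.20 | 0.411 | 0.408 |
| 0.25 | 0.560 | 0.555 |
| 0.30 | 0.681 | 0.686 |
| 0.35 | 0.792 | 0.793 |
| 0.40 | 0.873 | 0.872 |

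Every probability agrees to about 0.005. The fix leaves this table unchanged as a function of the rate; it changes which events count.

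**6. Suspension probability if a share f of events is exempted.** The documents give no f, so this is illustration only. The rule then sees p(1-f). From patient 1 with p = 0.30, the suspension probability is 0.686 (f = 0), 0.610 (10%), 0.483 (25%) and 0.259 (50%).

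Section 5.5 reports no dose-limiting toxicities in the first 5 patients. Assume this means 0 counted events in 5. The 2-event threshold can then no longer be met, since only patient 6 remains under it. Let X be events in patients 6 to 9 and Y events in patients 10 to 12:

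P(suspend) = P(X>=3) + P(X=2)P(Y>=2) + P(X=1)P(Y=3)

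- Counted rate 0.30: 0.0837 + 0.2646 x 0.216 + 0.4116 x 0.027 = 0.152
- 0.27 (f = 10% of 0.30): 0.0628 + 0.2331 x 0.1793 + 0.4201 x 0.0197 = 0.113
- 0.25 (f = one sixth): 0.0508 + 0.2109 x 0.1562 + 0.4219 x 0.0156 = 0.090
- 0.20 (f = one third): 0.0272 + 0.1536 x 0.104 + 0.4096 x 0.008 = 0.046

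**The case against.** The strongest reply is that the word is a slip. Where the booster is clearly meant, the text qualifies it as a boost or a poliovirus booster; the bare term occurs only in this exception. The list concerns toxicity of the study drug, and its autoimmune criterion is timed from infusion. Investigators may already read the exception that way. This stands as a plausible account of intent, but nothing in the protocol states it, and the literal reading points to another event.

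It is also fair that exclusion 12 removes patients with worsening steroid myopathy, that the rationale speaks of steroids alone, that virus-type paresis would more naturally fall under the neurologic-deficit exception, and that exempted events still appear in the adverse-event summaries of Section 15.4.2. All four reduce the practical risk. None changes the operative condition.

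Two stronger readings are tempting. A reader might infer that the protocol definitely starts the window at the booster and that up to 93% of the exposure precedes the drug. The documents do not support this: the term is undefined, and 93% is calendar time at the extreme booster date. A reader might also use Table 5 to infer a fall in suspension probability from 0.681 to 0.560 or 0.411. That needs one sixth or one third of all unacceptable toxicities to be wrongly exempted, for which the documents give no basis. It also starts the trial at patient 1, whereas five patients had already been treated.

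**Conclusion.** The point holds as an undefined start date in a rule that feeds the primary endpoint and the suspension count. Read literally, steroids stopped before infusion could exempt Grade 3-4 weakness or Grade 3 weight gain after PVSRIPO. Whether anyone applies it so is not known.

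The events at risk are few: severe weakness or weight gain within 14 days of infusion that would otherwise count, in a patient with supraphysiologic steroids after the booster and none after infusion. The supportable size is 8.3 percentage points per misclassified event at full accrual, and the possible loss of one event at a Table 4 threshold. The suspension-probability figures depend wholly on an assumed exempted share; those for the remaining patients also assume no counted event in the first five. They show direction and are not estimates. Because the sample is small and the correction cheap, it should be made.

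**What to change.** In the muscle-weakness and weight-gain exception of Section 9.1.5, replace 'the immunization' with 'the PVSRIPO infusion', in line with the 14-day post-infusion endpoint window. Use the same start date for the Table 4 count and the Section 15.4.2 percentage, and re-check any weakness or weight-gain events already exempted, including in patients treated so far.

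The cost is a one-phrase amendment and a short review of existing classifications. The downside is small: weakness truly due to steroids stopped shortly before infusion could be counted as unacceptable. The change does not settle whether steroids given after infusion should exempt an event without a judgement of cause. The sponsor could state that in the same amendment.
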